10 SAFETY ANALYSES

Safety analyses will be performed for the Safety population and will be descriptive and narrative in nature, including definitions of severity and relation for all adverse events, and focusing on serious adverse events.

The number and percent of patients with any adverse event, any serious adverse event, any adverse event related to the study device, and any adverse event related to study procedure will be presented. Summaries will be presented by study stage and overall.

No formal hypothesis testing will be performed.

11 Adverse Events

All adverse events (AEs) collected between the index procedure and the 6 weeks (+/-2 weeks) follow-up visit will be recorded in the eCRFs and will be reported. All adverse events (AEs) will be coded using the standardized Medical Dictionary for Regulatory Activities (MedDRA) central coding dictionary, version 24.0 or later. The analysis is performed on the safety population.

11.1 All Adverse Events

Summaries of incidence rates of individual AEs by System Organ Class (SOC) and Preferred Term (PT) will be prepared. Because a subject may experience more than one AE, summaries will provide both the number of subjects experiencing at least one event and the number of events within a reporting period. Percentages provided will be the percent of subjects experiencing one or more adverse events. In addition, incidence of AEs will be presented by severity (mild, moderate, severe) and by relationship to investigational product. Subjects experiencing an event within a given PT and SOC more than once will be counted under the maximum severity/relationship experienced.

A listing of all adverse events will include the subject number, AE number, days since index procedure, the AE SOC and PT, the severity of AE, whether or not the AE is classified as serious (SAE), the relationship of the AE to the investigational device or procedure, the action taken, the outcome, and the adjudication status.

11.2 Adverse Events Leading to Withdrawal

A summary of incidence rates (frequencies and percentages) of AEs leading to study withdrawal, by SOC will be prepared for the Safety Population. A data listing of AEs leading to withdrawal will also be provided, displaying details of the event(s) captured on the eCRF.

11.3 SERIOUS ADVERSE EVENTS

Summaries of incidence rates and relationship to the investigational device/procedure of individual SAEs by SOC and PT will be prepared. Summaries will provide both the number of subjects and the number of events within a reporting period. Percentages provided will be the percent of subjects experiencing one or more serious adverse events. A data listing of SAEs will also be provided, displaying details of the event(s) captured on the eCRF.

11.4 DEVICE DEFICIENCY

Data listings of device deficiencies will also be provided, displaying deficiency type, specification of device part, description, and whether associated with any AEs or SAEs.

11.5 (SERIOUS) ADVERSE DEVICE EFFECTS

Summaries of incidence rates of device and procedure related AEs by SOC and PT will be prepared. Summaries will provide both the number of subjects and the number of events within a reporting period. Percentages provided will be the percent of subjects experiencing one or more ADE events. Data listings of ADEs will also be provided, displaying details of the event(s) captured on the eCRF.

11.6 DEATHS

Should any subjects die during the course of the GATT-Patch trial, relevant information will be supplied in a data listing.

12 OTHER PLANNED ANALYSES

12.1 EXPLORATORY ENDPOINT ANALYSES

The exploratory endpoints will be analyzed on the FAS and PP populations. No formal hypothesis testing will be performed for these exploratory endpoints.

12.1.1 SURGERY TIME

Surgery time (minutes) will be presented as a summary table by reporting number of subjects, mean, standard deviation, median, quartiles, minimum, and maximum.

12.1.2 BLOOD LOSS

Blood loss during surgery (mL) will be presented as a summary table by reporting number of subjects, mean, standard deviation, median, quartiles, minimum, and maximum.

12.1.3 BLOOD TRANSFUSION

Blood transfusion during hospitalization (mL) will be presented as a summary table by reporting number of subjects, mean, standard deviation, median, quartiles, minimum, and maximum.

12.1.4 SBSS (0-5)

The Surface Bleeding Severity Score (SBSS) at the target bleeding site will be displayed on a 0-5 scale (0=none, 1=minimal, 2=mild, 3=moderate, 4=severe, 5=extreme). A summary table will be presented by reporting the frequencies and percentages of bleeding sites by each SBSS category (category 1, 2 and 3 are applicable for this study).

This exploratory analysis will be performed on the primary bleeding site. If there are multiple appropriate bleeding sites for one patient, this analysis will also be performed on all eligible bleeding sites that require topical hemostat application including the primary bleeding site.

12.1.5 HEMOSTATIC AGENTS/TECHNIQUES

The use of adjunct hemostatic agents and/or techniques (e.g. cautery, sutures, or staples) will be presented as a summary table by reporting the frequencies and percentage.

This exploratory analysis will be performed on the primary bleeding site. If there are multiple appropriate bleeding sites for one patient, this analysis will also be performed on all eligible bleeding sites that require topical hemostat application including the primary bleeding site.

12.1.6 Amount of Material needed versus Bleeding Surfaces

Amount of material needed versus bleeding surfaces will be presented as a summary table by reporting number of bleeding sites, mean, standard deviation, median, quartiles, minimum, and maximum of the number of patches applied per cm² bleeding surface.

This exploratory analysis will be performed on the primary bleeding site. If there are multiple appropriate bleeding sites for one patient, this analysis will also be performed on all eligible bleeding sites that require topical hemostat application including the primary bleeding site.

12.1.7 USER SATISFACTION

User satisfaction is reported by the surgeons completing system usability scale (SUS) and medical device specific questionnaires with 5 response options from Strongly disagree to Strongly agree. Number and percentage of subjects in each response category will be reported for both questionnaires.

For the medical device specific questionnaire, the number and percentage of subjects with any neutral, agree or strongly agree responses will also be reported.

SUS includes 10 questions. The number and percentage of subjects with any neutral, agree or strongly agree responses will also be reported for the odd numbered questions. For the even numbered questions, the number and percentage of subjects with any neutral, disagree or strongly disagree responses will be reported. In addition, total SUS score will be presented by reporting number of subjects, mean, standard deviation, median, quartiles, minimum, and maximum.

12.2 PLANNED SUBGROUP ANALYSES

The number and percentage of bleeding sites achieving hemostasis at 30, 60 and 180 seconds will be summarized for the following variables. Difference of percentages between the groups will also be reported including 95% CIs based on Wilson's method with continuity correction.

- Gender (Male vs Female)
- Age (< median vs ≥ median)
- SBSS category (1/2/3)
- Antiplatelet/ anticoagulant use at baseline (Yes vs No)
- Transected parenchyma area (< median vs \geq median)
- Bleeding surface area (< median vs ≥ median)
- Type of hepatic parenchyma (Normal/ Cirrhotic/ Staetotic)
- Type of bleeding (Venous/ Arterial/ Mixed)

Subgroup analyses will be performed on the primary bleeding site. If there are multiple appropriate bleeding sites for one patient, the analyses will also be performed on all eligible bleeding sites that require topical hemostat application including the primary bleeding site. In the case of multiple bleeding sites per patient, to account for the correlation within patient, the 95% CI will be estimated using a repeated measures logistic regression model. An unstructured covariance matrix will be used. In the event that the model fails to converge, the compound symmetry covariance matrix will be used.

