4 SAMPLE SIZE

The plan is to enroll and treat the following number of subjects across two stages:

- Stage I: maximum of 12 subjects
- Stage II: 39 subjects (36 evaluable subjects, assuming 7.5% drop-out rate),

Therefore, the current plan is to treat a total of up to 51 (=12+39) subjects with GATT-Patch. A maximum of 153 replaceable subjects may be enrolled.

Note that the number of Stage II subjects may increase to a maximum of 61 treated subjects (56 evaluable subjects, assuming 7.5% drop-out rate) if a sample size increase is deemed necessary based on the interim sample size re-estimation. Therefore, the total sample size may increase to a maximum of 73 (=12+61) treated subjects based on the interim sample size re-estimation.

The sample size of Stage II is powered on the primary endpoint to allow for assessment of noninferiority of GATT-Patch compared to the current knowledge (literature-based) of standard of care regarding the percentage of subjects achieving hemostasis at 3 minutes.

Assuming the true percentage of subjects achieving hemostasis at 3 minutes using GATT-Patch is 89%, then an evaluable sample size of 36 evaluable subjects from Stage II achieves over 90% power to demonstrate non-inferiority of GATT-Patch compared to current (literature-based) knowledge of standard care (i.e., demonstrate that the percentage achieving hemostasis at 3 minutes for the population treated with GATT-Patch is significantly greater than the performance goal of 65.4%) using a one-sided continuity corrected Z-test of proportion. The sample size considers the interim analysis of the primary performance endpoint (performed when approximately 69% of the planned evaluable Stage II subjects are treated, i.e., n≈25 evaluable Stage II subjects) based on a group sequential design to allow for possible early stopping for overwhelming performance success. The Lan- DeMets approach with an O'Brien-Fleming alpha-spending function is used to control the overall Type I error rate of the study at a one-sided 0.025 level.

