If the study does not stop for overwhelming performance success at the interim review, then an unblinded conditional power calculation and sample size re-estimation will also be conducted at the interim review. The sample size re-estimation analysis will be performed by an independent statistician according to the Mehta-Pocock Promising Zone approach. The conditional power for demonstrating that the primary performance endpoint is significantly greater than performance goal of 65.4% will be calculated under the current protocol-specified evaluable sample size (n=36), under the assumption that the observed interim treatment effect (i.e., percentage achieving hemostasis at 3 minutes) is the true treatment effect size. If the conditional power under the protocol-specified evaluable sample size is between 39% to <90% (the promising zone), the evaluable sample size may increase to maintain conditional power of 90%. The sample size may increase to a maximum of 56 (i.e., 20 additional) evaluable subjects for Stage II. Such a sample size increase based on the Mehta-Pocock Promising Zone approach will not require an additional penalty to the final significance (alpha) level.

The performance goal was established on a systematic literature review and meta-analysis (see CIP, Section 5.6), that found the lower 95% confidence interval of the random-effects meta-analytical

estimate of the percentage achieving hemostasis at 3 min to be 65.4%, based on previous studies for hemostatic techniques used in open liver surgery. The assumption of the true rate of hemostasis at 3 minutes being 89% for GATT-Patch is based on the pre-clinical evidence and clinical judgement.

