9.2 SECONDARY ENDPOINT ANALYSIS

The secondary performance endpoints will be determined using the FAS and PP population. The secondary endpoint analysis will be performed on the primary bleeding site. If there are multiple appropriate bleeding sites for one patient, this analysis will also be performed on all eligible bleeding sites that require topical hemostat application including the primary bleeding site.

The number of observations, mean, standard deviation, median, quartiles, minimum, and maximum time to hemostasis (seconds) will be presented, including the 95% CI of the mean. To account for the correlation within patient, when there are multiple bleeding sites available for one patient, the 95% CI will be estimated using a repeated measures linear regression model. An unstructured covariance matrix will be used. In the event that the model fails to converge, the compound symmetry covariance matrix will be used.

The number and percentage of bleeding sites achieving hemostasis at 30, 60, 90, 120, and 150 seconds, as well as the number and percentage of bleeding sites whichfail to reach hemostasis at 5 minutes will be presented. The 95% CI of the percentages based on Wilson's method with continuity correction will also be reported. To account for the correlation within patient, when there are multiple bleeding sites available for one patient, the 95% CI will be estimated using a repeated measures logistic regression model. An unstructured covariance matrix will be used. In the event that the model fails to converge, the compound symmetry covariance matrix will be used.

There will be no formal hypothesis testing on the secondary performance endpoints.

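### SAP 12.2 splits age and both area measures at the sample median and compares subgroups only on yes/no hemostasis at three times, which discards information the trial already collects

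*SAP*

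**What the plan says.** For eight subgroup factors, SAP 12.2 states: "The number and percentage of bleeding sites achieving hemostasis at 30, 60 and 180 seconds will be summarized for the following variables". The contrast is then fixed: "Difference of percentages between the groups will also be reported including 95% CIs based on Wilson's method with continuity correction".

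Three factors are cut at the sample median. Two read "Age (< median vs ≥ median" and "Bleeding surface area (< median vs ≥ median", and transected parenchyma area is handled the same way. The other five are natural categories, for example "Antiplatelet/ anticoagulant use at baseline (Yes vs No". The section names no test, p-value, precision target or analysis population.

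Finer data exist elsewhere in the plan. Hemostasis is checked on a 30-second grid, and treatment counts as failed if the site is not dry at 5 minutes (SAP 3.2.1). Time is summarised as a number, but only overall: "maximum time to hemostasis (seconds) will be presented, including the 95% CI of the mean" (SAP 9.2; SAP 12.3.2 repeats this for the Safety population). SAP 8.1 treats age as continuous, and SAP 12.1.6 uses bleeding surface in cm².

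The planned size is "Stage II: 39 subjects (36 evaluable subjects, assuming 7.5% drop-out rate", and after re-estimation "The sample size may increase to a maximum of 56 (i.e., 20 additional) evaluable subjects for Stage II" (SAP 4).

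**The concern.** Two layers of information are removed before subgroups are compared. Each time to hemostasis becomes a yes/no at three points, and each of three numeric covariates becomes above or below a cut that depends on the sample. With about 39 subjects and few failures at 3 minutes, little is left to compare.

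The question matters for later use. Bleed size is a natural candidate for influencing time to hemostasis, and protocol 3.3 says the results serve CE marking and the design of a US trial. A real dependence on area would often appear as a wide interval around zero. A median taken from this sample also gives the next trial no transferable cut-off, whereas a slope or correlation on the measured scale can be carried forward. No other section routinely relates performance to these covariates: the regression in SAP 7.6 adds baseline covariates only if sites differ.

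**Working it through.** **1. Inputs.** Stage II: 39 treated, 36 evaluable, at most 56 evaluable; assumed 3-minute rate 89%; goal 65.4%; final one-sided level 0.0229 (SAP 4 and 9.1). The documents give no rate at 30 or 60 s and no subgroup effect size, so those are assumptions below.

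**2. The plan's own figure.** The documents state power only for the primary test. With the continuity-corrected Z-test, 30/36 gives z = (0.8333 - 0.654 - 1/72) / √(0.654 × 0.346 / 36) = 2.09, which rejects; 29/36 gives 1.74, which does not. Exact binomial power for at least 30/36 at 89% is 90.6% (90.7% with the interim look). The stated power of over 90% reproduces. Nothing comparable is stated for subgroups.

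**3. Expected failures at 3 minutes.** 39 × 0.11 = 4.3; 36 × 0.11 = 4.0; 56 × 0.11 = 6.2.

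**4. Most extreme median split with 4 failures.** I read the SAP interval as the Newcombe difference interval built from continuity-corrected Wilson limits (l, u):

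lower = d - √[(p₁ - l₁)² + (u₂ - p₂)²]; upper = d + √[(u₁ - p₁)² + (p₂ - l₂)²].

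For 19/19, (l, u) = (0.791, 1). For 16/20 it is (0.557, 0.934). With d = 0.20:
- lower = 0.20 - √(0.209² + 0.134²) = -0.048
- upper = 0.20 + 0.243 = +0.443

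| Split | Difference (points) | 95% CI (points) |
|---|---|---|
| 19/19 vs 16/20 | 20.0 | -4.8 to +44.3 |
| 20/20 vs 15/19 | 21.1 | -3.4 to +46.1 |
| 18/18 vs 14/18 | 22.2 | -4.2 to +48.1 |

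At the expected count, no median split excludes zero.

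**5. Where that stops being true.**
- Five or more failures of 39 occur with probability 43% at a true 89%.
- Five failures all in the group of 19 give +0.5 to +51.4, which excludes zero. Five in the group of 20 give -1.0 to +49.4; six there give a lower limit of +2.9.
- With unequal groups (N = 39), 4 failures all in a group of 16 or fewer give a lower limit of at least +0.6.
- At 56 evaluable, 6 failures in one half (28/28 vs 22/28) give +2.0 to +41.5.
- A true 84% vs 94% is shown in about 6% of trials (N = 36 or 39); a true 79% vs 99% in 28% (N = 36) to 32% (N = 39).

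**6. What the cuts cost.** Simulation at N = 39. Time is in 30-second categories to 300 s plus failure, with a proportional-odds effect of a normal covariate and 89% dry at 180 s at the average covariate value. A planned cut counts as detecting if its interval excludes zero; Spearman uses two-sided 0.05. Ranges are across repeat runs.

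| Odds ratio per SD; dry at 30 s | 180 s | 60 s | 30 s | Any of three | Spearman, continuous |
|---|---|---|---|---|---|
| 2.2; 50% | 8% | 26-30% | 30-32% | 40-44% | 64-66% |
| 3.3; 50% | 25-26% | 57% | 59-60% | 73-74% | 92-93% |
| 2.2; 80% | 7% | 14% | 21% | 25% | 45-46% |

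Across all profiles and effects tried, Spearman gains about 19 to 29 points over any of the three cuts. With no effect, any-of-three signals in 3-6% of runs and Spearman in 4-6%, so the gain is not bought with false signals.

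For a two-level split with odds ratio 2.2 per SD, any-of-three against a rank-sum comparison of grid times gives 45 vs 52%, 44 vs 47%, 35 vs 38% and 26 vs 30% (30, 50, 70 and 80% dry at 30 s). Across all runs the gain is about 3 to 10 points.

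A different model (exponential times, hazard ratio 1.75 per SD) keeps the ordering: 19% at 180 s, 34% at 60 s, 57% for rank-sum on the median split and 76% for Spearman on the continuous covariate.

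**The case against.** The three times are not arbitrary. The 180 s cut is the primary endpoint, and 30 and 60 s are prespecified secondary endpoints. They also match the application procedure in protocol 2.6, where a 30-second press is followed by a second one if needed. Reporting declared endpoints by subgroup is consistent and easy to read. This stands, and it is why the tables should be kept.

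The three cuts are reported together, so the fair comparator is any of the three rather than 180 s alone. This also stands. On that basis the gain for gender, antithrombotic use and the other categorical factors is small, and the case rests mainly on the three continuous covariates.

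The simulated effects are monotone, which suits a rank correlation; threshold or non-monotone effects were not tried. That limits how far the figures generalise, though the ordering held in two different models.

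A reader might infer that the 3-minute comparison cannot show a difference at all. The documents do not support that: the failure count varies, and step 5 lists ordinary outcomes that exclude zero. The result also depends on the interval chosen. For 15/19 vs 20/20 the uncorrected interval is +0.6 to +43.3, and Fisher's exact p is 0.047.

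A reader might also infer that the trial's conclusion is at risk. SAP 12.2 plans estimates without a test, and the success criterion in SAP 2 does not mention subgroups. Protocol 3.3 speaks of the trial's results, not of these tables. A wide interval is an honest report of imprecision; reading it as consistent performance would be the reader's error.

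**Conclusion.** The point holds as a modest improvement in efficiency. At the expected 4 failures, even the most lopsided median split leaves the planned 95% interval covering zero at N = 36 and N = 39. That statement applies to the expected count, near-equal halves and the continuity-corrected interval as read here.

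Replacing the median split and yes/no outcome by the continuous covariate and time to hemostasis raises the chance of detecting an age or area effect by about 19 to 29 points over any of the planned cuts. For two-level factors the time scale alone adds about 3 to 10 points. Both figures rest on assumed monotone effects and assumed time profiles, since the documents fix only the 3-minute rate. The consequence is imprecise exploratory estimates; the primary conclusion is unaffected.

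**What to change.** In SAP 12.2, keep the 30, 60 and 180 s percentage tables. For age, transected parenchyma area and bleeding surface area, add an exploratory analysis of the continuous value on the primary bleeding site: a Spearman or Kendall correlation with time to hemostasis, or a proportional-odds slope per SD, with a 95% CI. Rank sites not dry at 5 minutes as worst. Name no formal test.

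Optionally, report time to hemostasis on its 30-second scale for the categorical factors as well, treating SBSS 1/2/3 as ordered.

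The cost is a few sentences of SAP text and a few lines of code, with no new data. The downside is that a rank measure or odds ratio reads less directly than a difference in percentages, which the retained tables offset.

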12.3 Additional Analyses

12.3.1 PRIMARY PERFORMANCE ENDPOINT - MULTIPLE BLEEDING SITES

If there are multiple appropriate bleeding sites, the first encountered bleeding site that requires topical hemostat application will be considered for the primary analysis of the primary endpoint. An additional analysis on the primary endpoint will be performed on all eligible bleeding sites treated with GATT-Patch including the primary bleeding site. To account for the correlation within patient, the 95% CI will be estimated using a repeated measures logistic regression model. An unstructured covariance matrix will be used. In the event that the model fails to converge, the compound symmetry covariance matrix will be used.

12.3.2 TIME TO HEMOSTASIS - SAFETY POPULATION

The number of bleeding sites, mean, standard deviation, median, quartiles, minimum, and maximum time to hemostasis (seconds), including the 95% CI of the mean will be presented for Stage I and Stage II treated subjects (Safety population).

This analysis will be performed on the primary bleeding site. If there are multiple appropriate bleeding sites for one patient, the analysis will also be performed on all eligible bleeding sites that require topical hemostat application including the primary bleeding site. To account for the correlation within patient, the 95% CI will be estimated using a repeated measures linear regression model. An unstructured

covariance matrix will be used. In the event that the model fails to converge, the compound symmetry covariance matrix will be used.

